10. One week before the operation, there are signs of infection, body temperature rises $>37.5^{\circ}\text{C}$, blood WBC $>10.0 \times 10^9/\text{L}$;
11. History of antibiotic use 1 week prior to surgery (excluding preoperative shock medication);
12. Preoperative neoadjuvant patients

(iii) Exit criteria

1. Accompanied by other non-oncological conditions that make it impossible for the patient to continue to receive this treatment plan;
2. After enrolment in the study, patients who required emergency surgery due to intestinal obstruction, perforation, or bleeding, et al. prior to stoma closure;
3. Patients with pathologically confirmed distant metastases after rectal surgery, including liver, pelvis, ovary, peritoneum, and distant lymph node metastases;
4. Intraoperative exploration for middle and low rectal cancer in anus-preserving surgery for those who need combined organ resection;
5. After enrolment in the study, patients requested to withdraw from the study cohort for various reasons, or were unable to complete the study programme and follow-up for various reasons;
6. Anastomotic fistula, severe anastomotic stenosis (inability to pass through enteroscopy or oesophageal finger and inability to dilate via oesophageal finger) after radical rectal surgery.

IV. Study endpoints

(i) Primary study endpoints:

Incidence of major LARS after 6 months of stoma closure.

(ii) Secondary research endpoints:

1. Bacteriological sequencing 1 month after stoma closure

[figure not shown]
2. Anorectal function (LARS questionnaire, Wexner¹⁵ incontinence score, MSKCC¹³⁻¹⁴ bowel function questionnaire), Glazer pelvic floor muscle surface electromyography, and quality of life scores after 1 month of stoma return.

3. Recovery of postoperative bowel function

After reversal surgery, time to oral feeding, time to anal defecation after reduction surgery, and rate of intestinal obstruction (intestinal obstruction was defined as ,inability to tolerate food for more than 72 H or the need for re-fasting or gastrointestinal decompression) were observed.

V. Research design

The study was a prospective randomised design with simple randomised grouping, randomised by prior computer-generated random number tables. The expected recruitment cut-off date for all subjects was 1 November 2022, with a predictable sample size of 60 cases to be enrolled based on patient admissions to the hospital. The enrolment process is as follows

(i) Transanal reinfusion of stoma discharge

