1. General principles: All statistical tests will be two-sided, and $P < 0.05$ will be considered statistically significant for the differences tested. The description of quantitative indicators will calculate the mean, standard deviation, median, minimum value, maximum value, if it meets the normal variance chi-square, expressed as the mean \pm standard deviation, and use the t-test to compare the differences between the two groups; data that do not meet the normal variance chi-square are expressed as the median (quartile), and the rank sum test is used for comparison. Categorical indicators were described by the number of cases and percentages in each category, and the chi-square test was used to compare the differences between the experimental and control groups.

2. The main outcome indicators of the occurrence of LARS at 6 months after the

reduction were expressed as the number of cases (percentage), and the chi-square test was used to compare the differences between the experimental group and the control group.

Secondary outcome indicator colony species results will be tabulated based on the top 15 species in abundance using cumulative histograms to compare species composition differences between samples. Based on the species abundance information of each sample at the genus level, the top 50 genera of abundance will be selected, and the samples and species will be clustered based on the abundance information of each sample, and heat maps will be drawn. And Shannon diversity index, Simpson index and Chao1 richness index were calculated for Alpha diversity analysis Comparative analysis of microbial community composition of samples between different groups was performed using Beta diversity analysis.

Secondary outcome indicators Wexner score, MSKCC Bowel Function Questionnaire, and QLQ-C30 Quality of Life Scale scores were analysed for repeated-measures data between the two groups, Mauchly's test of sphericity was performed, and ordinary one-way ANOVA or multifactorial ANOVA was performed according to the test results.

x. schedule of visits

| | | | | | | |
|---------------------------------------|--------------------------------------|-------------------|-------------------------------------|--------------------------------------|---------------------------------------|---------------------------------------|

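### Section X calls any result with P < 0.05 statistically significant, secondary outcomes included, with no adjustment, testing order or exploratory label

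*Combined protocol and SAP*

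**What the plan says.** Section IV(i) names one primary endpoint: "Incidence of major LARS after 6 months of stoma closure". Section IX bases the sample size on it alone.

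Section IV(ii) lists the secondary endpoints in three groups:

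- **Flora:** sequencing at 1 month.
- **Function at 1 month:** "Anorectal function (LARS questionnaire", the Wexner score and the MSKCC questionnaire, followed by "Glazer pelvic floor muscle surface electromyography, and quality of life scores after 1 month of stoma return".
- **Recovery:** under "Recovery of postoperative bowel function", time to oral feeding, time to defecation and the obstruction rate.

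Section X(ii)2 expands the flora item: "Shannon diversity index, Simpson index and Chao1 richness index were calculated for Alpha diversity analysis". It continues: "Comparative analysis of microbial community composition of samples between different groups was performed using Beta diversity analysis". It also plans repeated-measures analysis of Wexner, MSKCC and QLQ-C30.

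The decision rule is in Section X(ii)1. "All statistical tests will be two-sided", and a result below 0.05 "will be considered statistically significant for the differences tested". The rule does not separate primary from secondary outcomes. No multiplicity adjustment, testing hierarchy or statement that secondary results are exploratory appears anywhere in the plan.

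**The concern.** This is a stated rule, not just an omission. Read literally, a P value of 0.04 on one diversity index has the same standing as a P value of 0.04 on major LARS. Calling an endpoint secondary does not limit what may be concluded from it, because Section X(ii)1 covers every test.

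The trial's stated aims make this matter more than usual. The last paragraph before Section II sets out to learn whether reinfusion helps bowel function recover, reduces complications and improves dysbiosis, as high-level evidence for practice. Dysbiosis and complications are measured only by secondary endpoints. If the primary test failed, a single nominally significant flora or recovery result could be reported, within the plan as written, as meeting a stated aim.

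**Working it through.** The plan gives no figure for the error rate over its secondary outcomes, so there is nothing of its own to reproduce here. The sample size in Section IX concerns the primary test only and does not enter the calculation.

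**Step 1. Count the comparisons, each outcome once.**

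| Group | Outcomes | Number | Source |
|---|---|---|---|
| Function, 1 month | LARS, Wexner, MSKCC, electromyography, quality of life | 5 | Section IV(ii)2 |
| Recovery | oral feeding, defecation, obstruction | 3 | Section IV(ii)3 |
| Flora | Shannon, Simpson, Chao1, beta diversity | 4 | Section X(ii)2 |

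The first two groups give 5 + 3 = 8. Adding flora gives 12. The four flora comparisons are an assumption: the text says the indices are calculated and the communities compared, but it names no test for any of them. Both counts are therefore carried forward.

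**Step 2. Set the error per test.** Each test is two-sided at 0.05. With no true effect, the chance of significance is 0.05 in either direction and 0.025 in favour of reinfusion.

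**Step 3. Independent tests.** The chance of at least one significant result among k tests is 1 − (1 − a)^k.

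- k = 12, either direction: 1 − 0.95^12 = 0.460
- k = 12, favouring reinfusion: 1 − 0.975^12 = 0.262
- k = 8, either direction: 1 − 0.95^8 = 0.337
- k = 8, favouring reinfusion: 1 − 0.975^8 = 0.183

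**Step 4. Correlated tests.** The documents give no correlation between outcomes, so a range is assumed. Test statistics were simulated as equally correlated standard normals (400,000 draws) and compared with 1.96.

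| Tests | Correlation | Either direction | Favouring reinfusion |
|---|---|---|---|
| 12 | 0 | 46% | 26% |
| 12 | 0.3 | 40% | 20% |
| 12 | 0.5 | 32% | 16% |
| 12 | 0.7 | 23% | 12% |
| 8 | 0 | 34% | 18% |
| 8 | 0.5 | 25% | 12% |

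**Step 5. Flora direction.** Beta diversity has no favourable direction. If any significant beta-diversity difference counts as favourable, the independent figure for 12 tests is 1 − 0.975^11 × 0.95 = 0.281. The plan defines no favourable direction for the other three indices either. If a difference either way on all four could be presented as improvement, the figure is 1 − 0.95^4 × 0.975^8 = 0.335. That is an upper case under independence, not the central one.

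**The case against.** The strongest reply is that the trial has one designated primary endpoint, with its own test and its own sample size, and that the rest are already called secondary. In a trial of 60 patients, unadjusted secondary P values are common, and formal adjustment would cost power for little gain. Much of this stands. The 5% error rate of the primary test is intact, and formal adjustment of the secondary outcomes is a trade-off that the plan need not make. What does not stand is that the label alone is enough, because Section X(ii)1 gives every test the same verdict.

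A reader might infer more than the documents support, in three ways:

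- **That the either-direction figures are the chance of a false claim of benefit.** They are not. The tests are two-sided, so half of each 5% favours control. Over 12 tests the chance of a result favouring reinfusion is 26% to 12% for correlations of 0 to 0.7.
- **That each questionnaire at each visit is a separate test, which would raise the count well above 12.** Section X(ii)2 plans repeated-measures analysis for Wexner, MSKCC and QLQ-C30, and LARS at 6 months supplies the primary endpoint. The documents do not fix a larger number.
- **That a failed primary accompanied by several false-positive secondaries is likely.** With no true effect, the chance of two or more significant results among 12 is about 12% to 13% over correlations of 0 to 0.7. If reinfusion does have some effect, significant functional results may be real.

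It is also fair to say that three bowel questionnaires in the same patients, or several indices from the same samples, may be strongly correlated. That lowers the figures, and is why 0.7 is shown.

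**Conclusion.** The point holds as a cheap improvement to the plan, not as a flaw in the primary analysis. The rule permits an unadjusted claim of significance on any secondary outcome.

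On the 12-test count, the chance of at least one such result under no effect is about one in four to just under one in two in either direction. It is about one in nine to one in four in favour of reinfusion. On the eight outcomes that need no assumption about flora testing, and for correlations of 0 to 0.5, the ranges are 34% to 25% and 18% to 12%.

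These sizes rest on three assumptions: one test per outcome, equal correlation between outcomes, and, for the count of 12, a between-group test on each flora measure. The conclusion that secondary claims are uncontrolled rests on none of them.

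**What to change.** Amend Section X(ii)1 to say three things:

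1. The term statistically significant applies only to the primary comparison of major LARS at 6 months after stoma closure.
2. All secondary results, including the repeated-measures analyses and the flora comparisons, are exploratory. They are reported as between-group estimates with 95% intervals and nominal P values.
3. No secondary result supports a conclusion of efficacy if the primary test is not significant.

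No multiplicity procedure for the secondary outcomes is needed. Permitting adjusted claims would sit badly with the exploratory label. Unless made conditional on the primary test, it would also still let a secondary result carry the conclusion after that test failed.

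The cost is a few sentences of analysis-plan wording, with no change to patients, visits or data. The downside is that no secondary result can be called statistically significant, however small its P value.

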To address this hypothesis, in the present study we propose to conduct a prospective, randomised controlled study in patients with protective stoma, aiming to investigate whether stimulation of stoma drainage fluid through the anus to an open intestinal segment prior to stoma closure is beneficial for the recovery of bowel function, reduction of complications and improvement of intestinal dysbiosis, and to provide high-level evidence for the clinic.

II. Purpose of the study

To analyse the occurrence of defecation complications, rectal function and quality of life indicators after collecting stoma discharge for anal re-infusion to patients after performing protective ileostomy in anus-preserving surgery for middle and low rectal cancer, so as to evaluate the impact of collecting stoma drainage fluid for anal re-infusion on the recovery of patients' intestinal function.

III. Subject of the study

(i) Inclusion criteria

1. Age: 18~75 years old, male or female;
2. Pathological diagnosis of adenocarcinoma of the rectum on preoperative biopsy;
3. Clinical staging was T1-4aN0-2M0;
4. No distant multiple metastases;
5. ECOG rating 0-2;
6. Cardiac, pulmonary, hepatic and renal functions met the criteria for surgical tolerance
7. Clinical diagnosis of middle and low rectal cancer, the lower edge of the tumour is within 10cm from the anal verge, and it is proposed to perform radical rectal surgery and prophylactic ileostomy at stage I, and intestinal closure at stage II;
8. Patients and their families were able to understand and willing to participate in this clinical study and signed an informed consent form.

(ii) Exclusion criteria

1. Previous history of malignant colorectal tumour or recently diagnosed combination of other malignant tumours;
2. Patients with combined intestinal obstruction, intestinal perforation, intestinal haemorrhage, etc. requiring emergency surgery;
3. Neighbouring organs requiring combined organ removal;
4. ASA classification \geq Grade IV and/or ECOG physical status score > 2 ;
5. Those who have serious liver and kidney dysfunction, cardiopulmonary dysfunction, coagulation dysfunction or combined serious basic diseases cannot tolerate the surgery;
6. Have a history of serious mental illness;
7. Pregnant or breastfeeding women;
8. Those who have a history of taking steroid drugs;

9. Patients with other clinical and laboratory conditions considered by the investigator to be inappropriate for participation in the trial;

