(1) Items: including LARS score, Wexner incontinence score, MSKCC bowel function questionnaire; quality of survival score. The questionnaire follow-up was conducted by a professional pelvic floor follow-up team. The investigators of the pelvic floor follow-up team had appropriate professional training and were unaware of the patient grouping. The method of answering the questionnaires was explained to the patients before the questionnaire assessment, and after detailed enquiry, the patients were asked to answer the questionnaires in a specific way.

(2) Time: before radical rectal surgery, 1 month after stoma closure, 3 months after stoma closure and 6 months after stoma closure.

Survival follow-up:

Patient survival at 1 year post-stoma closure, 2 years post-stoma closure, 3 years post-stoma closure, and 5 years post-stoma closure follow up.

VII. Observation indicators

1. Baseline information: gender, age, height, weight, ASA, past medical and treatment history, co-morbidities, laboratory tests and imaging.
2. Sequencing of intestinal flora: before radical rectal surgery, before stoma closure, and 1 month after stoma closure.
3. Perioperative period: also include time to first postoperative defecation, time to first postoperative semi-liquid diet, and incidence of postoperative intestinal obstruction.
4. Follow-up indicators: LARS syndrome score, Wexner score, MSKCC Bowel Function Questionnaire, QLQ-C30 Quality of Life Scale.

VIII. Signing of informed consent and registration of subjects

(i) Informed consent signing:

The study will be conducted in accordance with clinical trial protocols, GCP principles and the Declaration of Helsinki. The informed consent form will be signed by the PI or a qualified, trained and authorised clinical staff member. The trial process needs to be explained in detail to the subject and/or authorised person, and it is important to avoid over-informing and to give the subject and/or authorised person enough time to consider whether to participate or not. Subjects/authorised persons will be enrolled in the experimental group once they have agreed and signed the informed consent form. The original informed consent form is kept on file at the research centre and a copy is retained by the subject.

(ii) Subject registration

After signing the informed consent form, patients are registered with subject information, baseline data, and oncology-related data, which should include all data from the screening phase of this study.

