IX. Sample size calculation

The sample size was calculated using PASS 15 software, with the major LARS incidence rate at 6 months after stoma closure surgery as the primary outcome. Based on retrospective data from the authors' centre, the major LARS rate at 6 months after stoma closure surgery was estimated to be 14% in the stoma discharge reinfusion group and 47% in the control group. Thus, a sample size of 27 patients was required to achieve 80% power in detecting differences, with a two-sided level of significance of 0.05.

Assuming a dropout rate of up to 10%, 60 patients were enrolled.

X. Methods of statistical analysis

(i) Definition of analysis set

1. Full Analysis Set (FAS)

According to the basic principle of intentional analysis (ITT), all enrolled subjects who were given a randomisation number will be included in the FAS. the FAS is the primary dataset for the evaluation of the efficacy of this study.

2. Compliance with the programme set (Per-Protocol Set, PPS)

PPS is defined as all cases in which planned treatment and visits were completed as specified in the protocol and there were no protocol violations that significantly affected outcomes. Patients with protocol violations that significantly affect the protocol will be excluded from this analysis set. Protocol violations that significantly affect efficacy will be identified at the time of data review. PPS is a secondary data set for the efficacy evaluation of this study.

3. Safety Set (SS)

Cases that completed at least one safety evaluation data after enrolment constituted the safety population of this study. The safety population was the primary population for the safety evaluation of this study.

(ii) Methods of statistical analysis

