| sports event | Pre-radi cal rectal surgery | pre-discha rge | Pre-sto ma closure surgery | Post-sto ma closure 1 month | Post-sto ma closure 3 months | Post-sto ma closure 6 months |
| Demographic information | ✓ | | | | | |
| Baseline assessment | ✓ | | | | | |
| bacterial colony sequencing | ✓ | | ✓ | ✓ | | |
| Pelvic floor muscle examination | ✓ | | ✓ | ✓ | ✓ | ✓ |
| surgical treatment | | ✓ | | | | |
| postoperative pathology | | ✓ | | | | |
| postoperative follow-up | | | | ✓ | ✓ | ✓ |

| | | | | | | |
|--|---|--|---|---|---|---|
| rectal examination | | | ✓ | ✓ | ✓ | ✓ |
| Pelvic floor surface electromyography assessment | ✓ | | ✓ | ✓ | ✓ | ✓ |
| Functioning, quality of life questionnaire | ✓ | | | ✓ | ✓ | ✓ |

Schedule 1

LARS Bowel Function Questionnaire

Does the patient complain of abnormal bowel movements: Yes No
Patient complained of abnormal defecation as: increased frequency incontinence painful defecation inability to distinguish between gas and faeces other

Whether the patient is satisfied with the current state of defecation:
Satisfied Unsatisfied

Does the patient think that the current state of defecation affects daily life:

No effect Yes effect

Use of medication to improve bowel movements: Yes Name _____ No

Prophylactic fistula Yes No

Prophylactic Fistula Payback Time is time Year Month Day
No

1. Have you ever had uncontrollable flatulence (farting)?

| | |
|--------------------------------|---|
|  Never | 0 |
| points | |
| Yes, less than 1 time per week | 4 |
| points | |
| Yes, at least once a week | 7 |
| points | |

2. Have you ever had an accidental leakage of loose stool?

| | |
|--------------------------------|---|
|  Never | 0 |
| points | |
| Yes, less than 1 time per week | 3 |
| points | |
| Yes, at least once a week | 3 |
| points | |

3. How many times a day do you have a bowel movement?

| | |
|---|---|
|  More than 7 times per day (24 hours) | 4 |
| points | |
|  4~7 times per day (24 hours) | 2 |
| points | |
|  1~3 times per day (24 hours) | 0 |
| points | |
|  Less than 1 time per day (24 hours) | 5 |

points

4. Have you ever had to have another bowel movement within an hour of having one?

Never

0

points

Yes, less than 1 time per week

9 points

Yes, at least once a week

11

points

5. Have you ever had to flush to the loo because of an urgent bowel movement?

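### The primary chi-square is valid but leaves the scheduled pre-surgery LARS score unused; pre-specified adjustment for it may add a few points of power at little cost.

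*Combined protocol and SAP*

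**What the plan says.** The primary endpoint (Section IV) is "Incidence of major LARS after 6 months of stoma closure". Section X(ii)2 describes it by counts and percentages and states that "the chi-square test was used to compare the differences between the experimental group and the control group". That sentence speaks only of LARS at 6 months; I read it as major LARS, in line with Sections IV and IX. No regression, stratified test or covariate is planned for this outcome.

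Section VI lists the functional questionnaires, "including LARS score, Wexner incontinence score, MSKCC bowel function questionnaire; quality of survival score", and times them "before radical rectal surgery, 1 month after stoma closure, 3 months after stoma closure and 6 months after stoma closure". The visit schedule agrees: the row "Functioning, quality of life questionnaire" is ticked at the visit before radical surgery. The repeated-measures paragraph in Section X covers the Wexner, MSKCC and QLQ-C30 scores but not LARS, so the pre-surgery LARS score enters no analysis.

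Allocation is by simple randomisation (Section V), with no stratification. Section IX takes major LARS rates "estimated to be 14% in the stoma discharge reinfusion group and 47% in the control group" and concludes that "a sample size of 27 patients was required to achieve 80% power in detecting differences, with a two-sided level of significance of 0.05", raised to 60 enrolled for dropout of up to 10%.

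**The concern.** The outcome is a cut-off on a questionnaire score, and the same questionnaire is completed before surgery. If the early score predicts the later one, an analysis that conditions on it estimates the treatment effect with a smaller standard error and accounts for chance imbalance in that score, which simple randomisation of 60 patients does nothing to limit. With about 16 expected events and power near 80% only under a 33-point difference, a few points of power are worth having if they cost almost nothing. The decision has to be made before the data are unblinded: adjustment chosen after imbalance has been seen is open to challenge.

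**Working it through.** **Inputs.** From Section IX: 14% v 47%, two-sided 0.05, 80% power, 27 patients, 10% dropout, 60 in total. I take 27 as per arm and allocation as 1:1. Neither is stated, but 27/0.9 = 30 and 2 × 30 = 60. The association between pre-surgery LARS score and major LARS at 6 months is not in the documents and is varied below.

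**1. The plan's own figure.** With unpooled variance, n per arm = (1.960 + 0.842)² × [0.14×0.86 + 0.47×0.53] / 0.33² = 7.849 × 0.3695 / 0.1089 = 26.6, which rounds up to 27. For dropout, 54/0.9 = 60. Both figures reproduce.

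**2. Power of the planned test.**

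| Method | 27 per arm | 30 per arm |
|---|---|---|
| Pearson chi-square, exact enumeration | 78.9% | 81.7% |
| Pooled normal approximation | 76.5% | 80.9% |
| Chi-square with Yates correction | 68.1% | 73.9% |

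The pooled formula would ask for 29.3, so 30, evaluable patients per arm. Section X does not say whether a continuity correction applies. Without one, power is just under 80% at the planned evaluable number.

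**3. Expected events.** 27×0.14 + 27×0.47 = 3.8 + 12.7 = 16.5. One covariate is affordable. The chance of no events at all in the reinfusion arm is 0.86^27 = 1.7%, so an ordinary logistic fit will occasionally fail through separation. In simulation it failed in about 2% of trials.

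**4. Gain from adjustment.** Simulation with 54 patients, simple randomisation, 4,000 trials per scenario and one continuous baseline covariate. The adjusted analysis is the standardised risk difference from a logistic model, with a degrees-of-freedom corrected standard error and a t reference.

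| Assumed odds ratio per SD | Chi-square power | Adjusted power | Change |
|---|---|---|---|
| 1.0 (useless) | 77% | 76% | about -1 |
| 1.65 | 79% | 80% | about +1 |
| 2.2 | 77% | 80.5% | about +3 |
| 3.3 | 78% | 84% | about +6 |

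The Monte Carlo standard error of a single power figure is √(0.78×0.22/4000) = 0.65 points, which explains why the chi-square column wanders. It lies a little below 78.9% because simple randomisation does not fix the arms at 27 each.

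**5. Type I error.** In the same simulation it was 5.0-5.9% for the chi-square, 6.4-7.8% for the adjusted test with the plain influence-function standard error, and 5.0-6.6% with the corrected one. Part of the gain seen with the plain standard error would come from a liberal test.

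**6. A second model.** With a probit latent correlation between baseline score and outcome, 27 per arm and a likelihood-ratio test, adjusted against chi-square power was 79.2% v 79.4% at correlation 0, 78.9% v 78.2% at 0.2, 80.5% v 78.8% at 0.3, and 85.4% v 79.6% at 0.5. The pattern is the same: nothing or a point or two for a weak predictor, about six for a fairly strong one.

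**The case against.** The strongest reply is that nothing is broken. An unadjusted chi-square is valid in a randomised trial, and its error rate already allows for chance imbalance. That stands: a reader might infer that simple randomisation without adjustment biases the estimate, and the documents give no ground for it.

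A reader might also infer that precision is definitely being lost. That is not supported either. The pre-surgery score is taken with the tumour in place, before the resection whose consequences Schedule 1 is meant to grade. A weak association is plausible, and the gain could then be nil.

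It is tempting to add tumour height. Inclusion item 7 requires that "the lower edge of the tumour is within 10cm from the anal verge", but that is a yes/no threshold. The baseline list in Section VII does not name a recorded distance, and the documents do not state its prognostic value. A second covariate also costs more: with two useless covariates, simulated power was 76% against 78% for the chi-square.

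Nor is adjustment free. With about 16 events, the plain standard error is liberal, separation can occur, and a complete-case model would drop randomised patients who lack a baseline score, against the FAS definition in Section X(i). These objections hold against a loosely specified model. They are met by one covariate, a corrected standard error, a penalised fallback and a rule for missing baseline scores.

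Finally, adjustment does not make up for too few patients. If the true rates were 20% v 47% (an assumption), power at 27 per arm would be 56%, and still only 66% if the baseline score explained 20% of the outcome variance.

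**Conclusion.** This is an efficiency point, not an error. The plan schedules a baseline measure of its own primary outcome and then makes no use of it, in a trial whose power at the planned evaluable number is 78.9%. Over assumed odds ratios per SD from 1.0 to 3.3, adjustment changes power by about -1 to +6 points. The facts about the plan are certain; the size of the gain is not, because it rests on an association the documents do not report. The results also assume 27 evaluable patients per arm on average, 1:1 allocation, the Section IX rates and an uncorrected Pearson test as comparator. The possible loss is small beside the possible gain, so pre-specified adjustment is worth adopting, provided the small-sample correction is part of the specification.

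**What to change.** In Section X(ii)2, specify as the primary analysis a logistic regression of major LARS (score 30-42) at 6 months on group and continuous pre-surgery LARS score, in the FAS.

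- Report the standardised (marginal) risk difference with 95% CI and p-value, using a degrees-of-freedom corrected standard error and a t reference.
- If separation occurs, use a Firth-penalised fit.
- Replace a missing pre-surgery score by the overall mean, ignoring arm, so that no randomised patient is dropped for a missing covariate.
- Keep the unadjusted chi-square as a sensitivity analysis.
- Do not adjust for values measured just before stoma closure, because they follow the infusions.
- Add tumour distance only if it is recorded as a number before randomisation.

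The cost is SAP wording and modest extra programming, with no new data, visits or patients. The statistical price is about 1 point of power if the score is not prognostic, and a type I error that may sit slightly above 5% (5.0-6.6% in simulation, against 5.0-5.9% for the chi-square).
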